12.1.5 Subject Follow-up

Every attempt will be made to follow the subject until the AE is resolved or until the Investigator determines the subject has returned to an acceptable state of health.

12.2 Laboratory Evaluations

12.2.1 Reporting and Evaluation of Local Laboratory Test Results

The Investigator will review laboratory values promptly upon receipt of the laboratory report. After the review is completed, the Investigator will sign and date each laboratory report. The laboratory will provide normal reference ranges for the laboratory tests on the laboratory results report. A value is **normal** when it falls on or within the upper and lower limits of the reference range. A value is **abnormal** when it falls outside the upper or lower limit of the reference range. The Investigator will review all laboratory results for clinical significance and note the clinical significance of all abnormal laboratory findings in the subject's source records.

The Investigator must evaluate any change from pre-dose to post-dose in a laboratory test which represents a worsening of the subject's clinical state as to whether it meets the definition of an AE or SAE. Any change determined to meet the definition of an AE or SAE will be recorded in the AE section of the CRF, and an SAER form will be forwarded to MIP's designee if appropriate (see Appendix VIII).

12.2.2 Additional procedures by site

For this study, specific sites may collect additional data that may represent investigator or institutional standard of care. For example, pre- or post- treatment evaluations or any other preor post- treatment laboratory, imaging or other ancillary studies, obtained for pheochromocytoma or paraganglioma subject management. MIP may collect data or procedure information related to the subject's enrollment, diagnosis or inclusion decision. The same confidentiality afforded to protocol defined data will be respected. The criteria for additional data collection, if any, would be to enhance study analysis and data understanding.

12.2.3 Repeat Testing

At the discretion of the Investigator, additional blood or urine samples may be collected to repeat the evaluation of any lab test that yields an abnormal result post-dose that was not abnormal predose. Parameters will be monitored, as clinically indicated, until the value returns to the predose level or clinically stabilizes, or until the Investigator or physician of record determines that further follow-up is unnecessary.

12.3 Electrocardiogram evaluation

If a worsening from pre-dose to post-dose is observed, the ECG may be repeated at the discretion of the Investigator, in addition to obtaining an ECG at the other post-dose time points required by the protocol. The Investigator will assess any worsening from pre-dose to post-dose in the ECG for clinical relevance (i.e., to determine whether it meets the definition of an AE). Any changes determined to meet the definition of an AE will be reported in the AE section of the CRF.

12.4 Physical Examinations

If a worsening from pre-dose to post-dose is observed, the physical examination may be repeated at the discretion of the Investigator, in addition to obtaining a physical examination at the other post dose time points required by the protocol. Any change from pre-dose to post-dose will be documented in the subject's source records and transcribed onto the physical examination section of the CRF. The Investigator will evaluate any worsening at the post-dose physical examination for clinical relevance and to determine whether an AE has occurred. Any changes determined to meet the definition of an AE or SAE will be recorded on the AE section of the CRF, and an SAER form will be forwarded to the MIP's designee if appropriate (see Appendix VIII). Specific observations (signs), symptoms and/or laboratory information supporting these changes will also be documented.

12.5 Vital Signs

If a worsening from pre-dose to post-dose is observed, vital signs measurements may be repeated at the discretion of the Investigator, in addition to obtaining vital sign measurements at the other post dose time points required by the protocol. The Investigator will evaluate any worsening in vital signs for its clinical relevance as to whether it meets the definition of an AE or SAE. Any changes determined to meet the definition of an AE or SAE will be recorded in the AE section of the CRF, and an SAER form will be forwarded to MIP's designee if appropriate (see Appendix VIII).

13. STATISTICAL METHODS

The detailed prospective procedures for data analysis are described in the Statistical Analysis Plan. Any changes in the original statistical methodology will be documented in the final Clinical Study Report. All statistical analyses, except those for dosimetry, will be performed using SAS[®] statistical analysis software version 9.1 or greater.³⁹

13.1 Analysis Sets

Figure 2 is a flow diagram of the protocol defined analysis sets. The Enrolled Set includes all subjects who have provided signed informed consent. The Dosimetry Set and Safety Set include all subjects who received the Imaging Dose. Adverse Events prior to the Imaging Dose will be captured for all enrolled subjects and reported separately from treatment-emergent AEs. The Full Analysis Set is a subset of the Dosimetry Set / Safety Set, excluding subjects who did not receive at least the first Therapeutic Dose. Subjects whose therapeutic dose is decreased below studv 500 mCi. based on results of the dosimetry or hematological dose modifications are included in the Full Analysis Set. The Full Analysis Set will be used for the primary analysis of efficacy. The Per Protocol Set is a subset of the Full Analysis Set, excluding subjects who received only one Therapeutic Dose, who did not attend the 3 Month and 6 Month Efficacy Visits, or with major protocol violations. Major protocol violations are defined as those that could impact the efficacy evaluation such as a subject is ineligible, missing key data, received an unauthorized treatment, etc. Only subjects receiving both Therapeutic Doses and with sufficient follow-up for efficacy will contribute to the Per Protocol Set. Key efficacy endpoints, including the primary endpoint of the proportion of subjects experiencing a reduction in use of all antihypertensive medication for at least six months or two cycles, will be analyzed on the Per Protocol Set (in addition to the Full Analysis Set).

FIGURE 2: SCHEMATIC OF PROTOCOL DEFINED POPULATIONS

* Adverse Events prior to the Imaging Dose will be captured for all enrolled subjects and reported separately from treatment-emergent AEs.

13.2 Sample Size

The sample size for this study is 58 subjects in the Per Protocol Set, for which it is estimated that approximately 75 subjects may be enrolled. The one-sided alternative hypothesis of the study is that the proportion of subjects experiencing reduction in use of all antihypertensive medication by at least 50% for at least six months or two cycles is 0.25, against the null hypothesis that the proportion is 0.10. Sample size of 58 was based on a one-sided significance level of $\alpha = 0.025$ and power of 0.90 (90%).

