13.3.2 Efficacy Analysis

13.3.2.1 Primary Analysis: Reduction in use of antihypertensive medication

The primary endpoint in this study is the proportion of subjects, after a Therapeutic Dose of Ultratrace iobenguane I 131, with a reduction (including discontinuation) of all antihypertensive medication by at least 50% for at least six months or two cycles. The duration of benefit is measured by maximum duration as follows. A benefit duration period commences when the subject's medication is reduced to a level at or below 50% of baseline, and continues until the subject's medication rises above 50% of baseline. For purposes of illustration, the following examples are provided (Month refers to the number of months after the first Therapeutic Dose).

- Example 1: A patient experiences the clinical benefit from the beginning of Month 2 to the beginning of Month 4, and then again from the beginning of Month 5 to the beginning of Month 12. Since the maximum duration of the benefit was 7 months, the subject is considered a success on the primary endpoint.
- Example 2: A patient experiences the clinical benefit from the beginning of Month 2 to the beginning of Month 4, and then again from the beginning of Month 6 to the beginning of Month 11. The patient begins another anticancer treatment at Month 15 and is discontinued. Even though the patient experienced the clinical benefit for a total of 7 months, the maximum duration of the benefit was only 5 months, so the subject is considered a failure on the primary endpoint.
- Example 3: A patient experiences the benefit from the beginning of Month 2 to the beginning of Month 9. At Month 10, the patient receives another anticancer treatment and is discontinued from the study. Since the maximum duration of the benefit was 7 months, prior to discontinuation, the patient is considered a success on the primary endpoint.

For the primary analysis of the primary endpoint, a point estimate (with a 95% confidence interval, using the normal approximation with a continuity correction) for the proportion of subjects experiencing a reduction (including discontinuation) of all antihypertensive medication

by at least 50% for at least six months or two cycles will be calculated. This single-arm trial will be considered a success if the lower bound of the two-sided 95% confidence interval exceeds 0.10 (10%). The Full Analysis Set will be used for the primary analysis, but this same analysis will be repeated for the Per Protocol Set.

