6. DETERMINATION OF SAMPLE SIZE

The planned sample size for this study is 58 subjects, for which it is estimated that approximately 75 subjects may be enrolled. The one-sided alternative hypothesis of the study is that the proportion of subjects experiencing a reduction (including discontinuation) of all antihypertensive medications by at least 50% for at least six months or two cycles is 0.25, against the null hypothesis that the proportion is 0.10. Sample size was based on a one-sided significance level of $\alpha = 0.025$ and power of 0.90 (90%).

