- b. the date of the subject's last applicable recorded study-related disposition date. If the subject has discontinued the study prior to the end of the 12-Month Efficacy Phase due to any of the following reasons:
- Withdrew consent
 - Was lost to follow-up
 - Death
 - Withdrew due to progressive disease
 - Received other anticancer therapy
 - Experienced an adverse event resulting in study discontinuation

The last participation date is the corresponding disposition date within the 12-Month Efficacy Phase (i.e., date that the subject withdrew consent, was lost to follow-up, died, withdrew due to disease progression, received other anticancer therapy, or experienced an adverse event resulting in study discontinuation).

If the subject has completed the 12-Month Efficacy Phase but continues to meet the criteria of having a $\geq 50\%$ reduction of all antihypertensive medications, the last applicable disposition date would be the long-term follow-up completion/discontinuation date.

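### The stated 90% power belongs to 58 Per Protocol subjects, but success is decided on the Full Analysis Set, for which neither document gives a power

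*Protocol*

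**What the plan says.** Protocol 13.2 reads "The sample size for this study is 58 subjects in the Per Protocol Set", with about 75 subjects to be enrolled to reach it. The alternative response rate "is 0.25, against the null hypothesis that the proportion is 0.10", at one-sided alpha 0.025 and 90% power. The protocol outline (Section 4, Sample Size) says the same and also names the Per Protocol Set.

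The success decision is made on another set. Protocol 13.3.2.1: "The Full Analysis Set will be used for the primary analysis, but this same analysis will be repeated for the Per Protocol Set". Success requires the lower limit of a two-sided 95% interval to exceed 0.10. The outline and SAP 7.4 and 7.4.1 also place this decision on the FAS. The protocol computes the interval by a normal approximation with continuity correction; SAP 7.4.1 uses Agresti-Coull.

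SAP 6 reads "The planned sample size for this study is 58 subjects". It keeps 0.10, 0.25, 0.025 and 0.90 but does not say which set the 58 refers to. SAP 9 records that the Per Protocol label was taken out of this section in version 5.0.

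The FAS needs only the first Therapeutic Dose (Protocol 13.1, SAP 5.3). The Per Protocol Set (PPS) further excludes one-dose subjects, subjects without the Month 3 and Month 6 efficacy visits, and major violators (Protocol 13.1, SAP 5.4).

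**The concern.** A power statement is useful only if it describes the rule that decides the trial. Here the 0.90 is calculated for one set and the decision is taken on a larger one, with a different make-up and two candidate intervals.

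The extra FAS subjects may respond less often. Response needs 168 consecutive days of benefit (SAP 7.4.2). For subjects who leave before the end of the 12-month efficacy phase, the benefit period stops at the disposition date. The listed reasons include progression, other anticancer therapy, death and "Experienced an adverse event resulting in study discontinuation". A subject who leaves before day 168 after the first Therapeutic Dose cannot respond.

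At stake is how the result is read. A negative trial would be reported as having missed with 90% power, although the documents do not show that the success rule has that power.

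**Working it through.** **Inputs.** p0 = 0.10, p1 = 0.25, one-sided alpha 0.025, power 0.90, n = 58 (Protocol 13.2). FAS size N from 58 to 75: the upper end comes from Protocol 9.1, which has about 75 subjects dosed, and from 13.2 and SAP 6, which have about 75 enrolled. The response rate q in FAS subjects outside the PPS is not given; it is assumed here to lie between 0 and 0.25.

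**Step 1: the plan's own figure.** One-sample normal approximation:

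n = [(1.96·√(0.10·0.90) + 1.2816·√(0.25·0.75)) / 0.15]² = [(1.96·0.3000 + 1.2816·0.4330) / 0.15]² = 58.06.

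Power at n = 58 by the same formula is 0.8998. The plan's 58 and 0.90 therefore reproduce, as a normal-approximation calculation for 58 subjects at 0.25.

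**Step 2: responders required.** With z = 1.96, find the smallest r whose lower limit L exceeds 0.10.

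- SAP rule: ñ = N + z², p̃ = (r + z²/2)/ñ, L = p̃ − z·√(p̃(1−p̃)/ñ). At N = 58, r = 11 gives L = 0.1076 and r = 10 gives 0.0944, so 11 are needed.
- Protocol rule (usual 1/(2N) correction assumed): L = p̂ − z·√(p̂(1−p̂)/N) − 1/(2N). At N = 58, r = 13 gives L = 0.1082 and r = 12 gives 0.0940, so 13 are needed.

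**Step 3: exact power and alpha.** Responders are X + Y, with X ~ Bin(58, 0.25) and Y ~ Bin(N − 58, q) independent. Power is P(X + Y ≥ r). Exact one-sided alpha is P(Bin(N, 0.10) ≥ r). Setting q = 0.25 is the case of a 0.25 rate throughout the FAS.

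| N | SAP rule: r | alpha | power at q = 0 / 0.10 / 0.25 | Protocol rule: r | alpha | power at q = 0 / 0.10 / 0.25 |
|---|---|---|---|---|---|---|
| 58 | 11 | 0.0273 | 0.890 (no extras) | 13 | 0.0042 | 0.722 (no extras) |
| 65 | 12 | 0.0264 | 0.817 / 0.864 / 0.917 | 14 | 0.0044 | 0.610 / 0.685 / 0.782 |
| 70 | 13 | 0.0205 | 0.722 / 0.822 / 0.920 | 15 | 0.0035 | 0.490 / 0.627 / 0.794 |
| 75 | 13 | 0.0343 | 0.722 / 0.854 / 0.957 | 15 | 0.0068 | 0.490 / 0.678 / 0.873 |

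**Step 4: reading the table.**

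- With 0.25 throughout the FAS, power over N = 58 to 75 is 0.890–0.957 (SAP rule) or 0.722–0.873 (protocol rule).
- If all extras fail, the FAS rate is 14.5/70 = 0.207 or 14.5/75 = 0.193, and power is 0.722 or 0.490.
- At N = 75 the SAP rule reaches 0.90 once q is about 0.15 (0.899 at q = 0.15). The protocol rule would need q of about 0.28, above the assumed PPS rate.
- For N = 58 to 62 the SAP rule still needs 11 responders, so its power stays at 0.89 or more even if every extra fails.

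**The case against.** The strongest defence is that nothing is miscalculated. Sizing on evaluable subjects and enrolling more is common. The final SAP decides on the FAS by Agresti-Coull and no longer ties 58 to the PPS; read that way, 58 subjects at 0.25 give 0.89, essentially the stated 0.90. Protocol 13.5 expects the final SAP to carry changes from the protocol's analysis. This stands as far as it goes: the explicit mismatch of sets is in the protocol, and what the SAP leaves is an unnamed set.

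Three stronger readings are tempting, and the documents do not support them.

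- A reader might infer that the design's own alternative yields power as low as 72% or 49%. It does not. The 0.25 is stated for subjects, with no separate rate outside the PPS. Those floors also require 12 to 17 extra subjects, all non-responders. Seventeen is itself a maximum, because 75 enrolled need not mean 75 dosed.
- A reader might infer that the FAS rate must be below the PPS rate. That is plausible but not shown. SAP 7.4.2 asks for at least one Therapeutic Dose, so one-dose subjects can respond. Example 3 in SAP 7.4.1 counts an early leaver as a success. Missing an efficacy visit does not rule out 168 days of benefit, since medication use is recorded throughout.
- A reader might infer that power falls short under either interval because of the set. Under the protocol rule much of the loss comes from the interval: it gives 0.722 for 58 subjects in the PPS itself, and moving to 75 subjects at 0.25 raises this to 0.873.

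**Conclusion.** The point holds as a moderate one. The protocol attaches 0.90 to a set that does not decide the trial, the SAP attaches it to no named set, and the power of the FAS decision is stated nowhere.

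Under the protocol rule, 0.90 is missed at every FAS size from 58 to 75 for any non-PPS rate up to 0.25; the best case is 0.873. Under the SAP rule, power is adequate if 0.25 applies to the whole FAS. It may fall short if 0.25 applies only to the PPS: 82–85% at an assumed non-PPS rate of 0.10 and N = 70–75, with 72% as the extreme bound. The SAP rule's highest power, 0.957 at N = 75, comes with an exact one-sided alpha of 0.034 rather than 0.025.

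These figures rest on a PPS of exactly 58 responding at 0.25, independent outcomes, and assumed ranges for FAS size and non-PPS response.

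**What to change.** Keep the enrolment target; SAP 4.1 reports that enrolment closed in December 2015. In the protocol outline, Protocol 13.2 and SAP 6:

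1. Name the FAS as the set on which success is decided, and say which interval rule governs.
2. Say whether the 0.25 is a FAS rate or a PPS rate.
3. Replace the single 0.90 with the exact binomial power of the governing rule over FAS sizes 58 to 75 and an assumed non-PPS rate of 0 to 0.25.
4. List the responders required (SAP rule 11/58, 12/65, 13/70, 13/75; protocol rule 13, 14, 15, 15) with the exact one-sided alpha at each size.
5. Report the PPS power separately and label it as such.

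The cost is a few sentences and one small table. No subject, estimate or success threshold changes. The sponsor gives up a single favourable power figure for a range that may be less favourable.

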13.3 Statistical Methods

13.3.1 Descriptive and summary statistics

Summary tables and listings will be provided for demographic and baseline characteristics, including age, race, sex, height, weight, medical history, and prior medications. Summary tables and listings will also be provided for the number of subjects who have been enrolled and were administered imaging and therapy doses according to protocol guidelines.

Appropriate descriptive statistics will be generated for each endpoint of interest. In particular, mean, median, standard deviation and range will be computed for each continuous variable whilst counts and percentages will be computed for each categorical variable.

13.3.2 Efficacy Analysis

13.3.2.1 Primary Analysis: Reduction in use of antihypertensive medication

The primary endpoint in this study is the proportion of subjects, after a Therapeutic Dose of Ultratrace iobenguane I 131, with a reduction (including discontinuation) of all antihypertensive medication by at least 50% for at least six months or two cycles. The duration of benefit is measured by maximum duration as follows. A benefit duration period commences when the subject's medication is reduced to a level at or below 50% of baseline, and continues until the subject's medication rises above 50% of baseline. For purposes of illustration, the following examples are provided (Month refers to the number of months after the first Therapeutic Dose).

- Example 1: A patient experiences the clinical benefit from the beginning of Month 2 to the beginning of Month 4, and then again from the beginning of Month 5 to the beginning of Month 12. Since the maximum duration of the benefit was 7 months, the subject is considered a success on the primary endpoint.
- Example 2: A patient experiences the clinical benefit from the beginning of Month 2 to the beginning of Month 4, and then again from the beginning of Month 6 to the beginning of Month 11. The patient begins another anticancer treatment at Month 15 and is discontinued. Even though the patient experienced the clinical benefit for a total of 7 months, the maximum duration of the benefit was only 5 months, so the subject is considered a failure on the primary endpoint.
- Example 3: A patient experiences the benefit from the beginning of Month 2 to the beginning of Month 9. At Month 10, the patient receives another anticancer treatment and is discontinued from the study. Since the maximum duration of the benefit was 7 months, prior to discontinuation, the patient is considered a success on the primary endpoint.

For the primary analysis of the primary endpoint, a point estimate (with a 95% confidence interval, using the normal approximation with a continuity correction) for the proportion of subjects experiencing a reduction (including discontinuation) of all antihypertensive medication

by at least 50% for at least six months or two cycles will be calculated. This single-arm trial will be considered a success if the lower bound of the two-sided 95% confidence interval exceeds 0.10 (10%). The Full Analysis Set will be used for the primary analysis, but this same analysis will be repeated for the Per Protocol Set.

13.3.2.2 Secondary Analyses

13.3.2.2.1 Overall Tumor Response per RECIST Criteria

Objective tumor response and overall tumor response will be assessed according to the Response Evaluation Criteria in Solid Tumors (RECIST).⁴³ Tumor size measurements will be obtained by CT or MR at baseline and at 3, 6, 9, and 12 months post-treatment. For each subject, the same modality (CT or MR) and the same technique used for the baseline assessment will be used in all subsequent assessments.

Measurable lesions are lesions that can be accurately measured in at least one dimension with longest diameter ≥ 20 mm using conventional techniques or ≥ 10 mm with spiral CT scan. Non-measurable lesions are all other lesions, including small lesions (longest diameter < 20 mm with conventional techniques or < 10 mm with spiral CT scan), or bone lesions, leptomeningeal disease, ascites, pleural/pericardial effusion, inflammatory breast disease, lymphangitis cutis/pulmonis, cystic lesions, and also abdominal masses that are not confirmed and followed by imaging techniques.

At baseline, all measurable lesions up to a maximum of 5 lesions per organ and 10 lesions in total, representative of all involved organs, should be identified as target lesions and recorded and measured. Target lesions should be selected on the basis of their size (lesions with the longest diameter) and their suitability for accurate repeated measurements (either by imaging techniques or clinically). A sum of the longest diameter (SLD) for all target lesions will be calculated and reported as the baseline SLD. The baseline SLD will be used as reference by which to characterize the objective tumor. All other lesions (or sites of disease) should be identified as non-target lesions and should also be recorded at baseline. Measurements of these lesions are not required, but the presence or absence of each should be noted at each follow-up.

Objective tumor response criteria for target lesions are as follows:

Complete Response (CR)	Confirmed* disappearance of all target lesions
Partial Response (PR)	Confirmed* decrease of at least 30% in the SLD of target lesions, taking as reference the baseline SLD
Moderate Response (MR)	Confirmed* decrease of at least 15% but at most 29% in the SLD of target lesions, taking as reference the baseline SLD
Stable Disease (SD)	Changes do not meet the criteria for CR, PR, MR or PD
Progressive Disease (PD)	At least a 20% increase in the SLD of target

lesions, taking as reference the smallest SLD recorded since the treatment started or the appearance of one or more new lesions

Objective tumor response criteria for non-target lesions are as follows:

Complete Response (CR)	Confirmed* disappearance of all non-target lesions
Incomplete Response/ Stable Disease (SD)	Persistence of one or more non-target lesion(s)
Progressive Disease (PD)	Appearance of one or more new lesions and/or unequivocal progression of existing non-target lesions

Overall tumor response combines assessment of target lesions and non-target lesions. At each assessment, overall tumor response is that shown in the "Overall Response" column below.

Target lesions	Non-Target Lesions	New Lesions	Overall Response
CR*	CR*	No	CR
CR*	Incomplete response/SD	No	PR
PR*	Non-PD	No	PR
MR*	Non-PD	No	MR
SD	Non-PD	No	SD
PD	Any	Yes or No	PD
Any	PD	Yes or No	PD
Any	Any	Yes	PD

* To be assigned a status of CR, PR or MR, changes in tumor measurements must be confirmed by repeat assessments that should be performed no less than 4 weeks after the criteria for response are first met.

For each post-therapy visit where objective tumor response is evaluated, each subject will be assigned one of the following categories: 1) complete response, 2) partial response, 3) moderate response, 4) stable disease, 5) progressive disease, or 6) unknown (not assessable, insufficient data) based upon the independent, central evaluation of scans. An overall response of CR, PR or SD meets the secondary endpoint criterion for overall tumor response. RECIST tumor measurements will be listed by target, non-target, and bone (also considered non-target) lesions, for each RECIST reviewer, and the adjudicator, if there was a discrepant result for the overall tumor response. A summary table will be provided showing by nominal time point, target, non-target, bone, and overall response. Figures will also be constructed showing the sum of the longest diameter (SLD) over time since therapeutic dose.

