Endpoints:	 Primary Endpoint: The primary endpoint for this trial is the proportion of study subjects with a reduction (including discontinuation) of all antihypertensive medication by at least 50% for at least six months or two cycles Ultratrace iobenguane I 131. The primary endpoint will be assessed at the time of study completion or discontinuation, whichever occurs first. Secondary Endpoints: Proportion of subjects with overall tumor response of CR or PR per RECIST criteria, Proportion of subjects with overall tumor response of CR, PR or MR (moderate response) per RECIST criteria Bone lesion response per the Soloway Scale Tumor marker response in 24 hr urine and other serum/plasma tumor markers associated with pheochromocytoma/paraganglioma Status of hypertension and changes in blood pressure Quality of Life per the recommended guidelines from the EORTC
	 QLQ-C30 manual Symptoms as evaluated through the NIH Quality of Life and Symptoms Questionnaire for Pheochromocytoma and Paraganglioma
	Change in use of analgesics and pain medications
	• Overall survival (OS), defined as the time from the date of enrollment to the date of death from any cause. OS time will be censored at the last date the subject is known to be alive when the confirmation is absent or unknown.
	 Safety assessed by changes in lab values, physical exams or vital signs, and the occurrence of treatment emergent adverse events Human radiation absorbed dose estimates to normal organs
Sample Size:	It is anticipated that approximately 75 subjects will be enrolled to ensure that 58 subjects receive two doses and are evaluable for safety and efficacy. The one-sided alternative hypothesis of the study is that the proportion of subjects experiencing a reduction (including discontinuation) of all antihypertensive medication by at least 50% for at least six months or two cycles is 0.25, against the null hypothesis that the proportion is 0.10. Sample size of 58 subjects in the Per Protocol Set was based on a one-sided significance level of $\alpha = 0.025$ and power of 0.90 (90%).
Statistical Methods:	Summary tables and listings of demographics and baseline characteristics for all enrolled subjects will be presented. Listings of laboratory test results collected at baseline and during the study will be generated.

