8. STUDY OBJECTIVE

The primary and secondary objectives of this study are as follows.

Primary Objective:

To determine the proportion of study subjects with a reduction (including discontinuation) of all antihypertensive medication by at least 50% for at least six months or two cycles, from two Therapeutic Doses each at 500 mCi (or 8 mCi/kg, for subjects weighing 62.5 kg or less) of Ultratrace Iobenguane I 131 administered approximately three months apart.

Secondary Objectives:

- To evaluate the safety of Ultratrace iobenguane I 131 in subjects with malignant pheochromocytoma/paraganglioma, including human radiation absorbed dose estimates to normal organs.
- To assess the proportion of subjects with overall tumor response of CR or PR per RECIST criteria
- To assess the proportion of subjects with overall tumor response of CR, PR or MR (moderate response, i.e., decrease in the sum of the longest diameters of the target lesions of 15-30%, with no evidence of PD in non-target lesions) per RECIST criteria
- To assess bone lesion status on the Soloway Scale
- To assess tumor marker response in 24 hr urine and other serum/plasma tumor markers associated with pheochromocytoma/paraganglioma
- To describe changes from baseline in the overall quality of life through the EORTC QLQ-C30 questionnaire post-treatment
- To describe changes from baseline in symptoms using the NIH Quality of Life and Symptoms Questionnaire for Pheochromocytoma and Paraganglioma post-treatment
- To assess change in use of analgesics and pain medications
- To describe Karnofsky Performance Status post-treatment
- To assess overall survival, up to 5 years post-treatment

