4.3. Trial Objectives: Secondary

The secondary objectives of this trial are as follows:

- To evaluate the safety of iobenguane I 131 in subjects with malignant pheochromocytoma/paraganglioma, including human radiation absorbed dose estimates to normal organs.
- To assess the proportion of subjects with overall tumor response of CR or PR per RECIST criteria.
- To assess the proportion of subjects with overall tumor response of CR, PR or MR (moderate response, i.e., decrease in the sum of the longest diameters of the target lesions of 15-30%, with no evidence of progressive disease [PD] in non-target lesions) per RECIST criteria.
- To assess status of bone lesions using the Soloway Scale.
- To assess tumor marker response in 24 hr urine and other serum tumor markers associated with pheochromocytoma/paraganglioma.
- To describe changes from baseline in the overall QoL through the EORTC QLQ-C30 questionnaire post-treatment.
- To describe changes from baseline in symptoms using the NIH Quality of Life and Symptoms Questionnaire for Pheochromocytoma and Paraganglioma post-treatment.
- To assess change in use of analgesics and pain medications.
- To describe Karnofsky Performance Status post-treatment.
- To assess overall survival, up to 5 years post-treatment.

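### Protocol 13.3.2.2.1 counts stable disease, and not moderate response, toward the tumor-response endpoint; the SAP points to the right definitions but never withdraws the sentence

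*Protocol*

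**What the plan says.** The Secondary Endpoints in Protocol Section 4 list two tumor-response measures: "Proportion of subjects with overall tumor response of CR or PR per RECIST criteria" and "Proportion of subjects with overall tumor response of CR, PR or MR (moderate response) per RECIST criteria". Protocol Section 8 sets matching objectives, the first being "To assess the proportion of subjects with overall tumor response of CR or PR per RECIST criteria". SAP 4.3 repeats both; the second begins "To assess the proportion of subjects with overall tumor response of CR, PR or MR".

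Protocol 13.3.2.2.1 assigns each subject, at each post-therapy visit, to one of six categories: CR, PR, MR, SD, PD or unknown. For target lesions it defines SD as the remainder: "Changes do not meet the criteria for CR, PR, MR or PD". After the category list it gives the responder rule: "An overall response of CR, PR or SD meets the secondary endpoint criterion for overall tumor response".

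Protocol Section 13 hands the detail to the SAP: "The detailed prospective procedures for data analysis are described in the Statistical Analysis Plan". SAP 7.4.5 does not repeat the responder sentence. It plans one frequency table on standard RECIST, with MR subjects placed in SD, and another on modified RECIST with MR shown. SAP Section 11 lists both tables. SAP 7.4.7 codes best RECIST response as CR/PR against SD/PD for one cross-tabulation with tumor markers. SAP 7.4.5 does not say which categories make up either secondary proportion.

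**The concern.** The only explicit responder rule in the protocol's tumor-response analysis section matches neither endpoint. It adds a category that both endpoints leave out (SD) and omits one that the second endpoint includes (MR). Anyone deriving the proportion from that section would report something close to disease control under the name of tumor response, and would drop confirmed moderate responders. In a single-arm study there is no comparator to reveal the inflation. The primary endpoint, its sample size and the success rule do not depend on this sentence.

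**Working it through.** The plan states no figure for this endpoint, so there is nothing to reproduce. The check sets the definitions side by side.

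**Categories counted as response (six categories of Protocol 13.3.2.2.1)**

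| Category | Endpoint 1 | Endpoint 2 | Sentence in 13.3.2.2.1 |
|---|---|---|---|
| CR | yes | yes | yes |
| PR | yes | yes | yes |
| MR | no | yes | no |
| SD | no | no | yes |
| PD | no | no | no |
| Unknown | no | no | no |

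The sentence differs from endpoint 1 on one category of six (SD added) and from endpoint 2 on two of six (SD added, MR left out).

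**Can SD be read as including MR?** Not in this section. MR has its own row in the criteria table and its own place in the category list, and SD is defined as excluding it.

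**Worked cases** (decrease confirmed where required, non-target lesions not progressing, no new lesions):
- 5% decrease: SD, meets the sentence.
- 20% decrease: MR, fails the sentence.
- 30% decrease: PR, meets the sentence.

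**Size.** Let p_SD and p_MR be the shares of subjects in SD and MR, with MR kept separate.
- Sentence minus endpoint 1 = (CR + PR + SD) − (CR + PR) = p_SD.
- Sentence minus endpoint 2 = (CR + PR + SD) − (CR + PR + MR) = p_SD − p_MR. This is negative if MR is the more common category.

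The documents give neither share for this trial. As an illustration only, take 58 subjects (the planned Per Protocol number), CR + PR of 22% (the rate the protocol cites from a phase II series of 49 evaluable patients), and assumed shares of 5% to 15% for MR and 30% to 60% for SD:
- Endpoint 1: 58 × 0.22 = 12.8, about 13.
- Endpoint 2: 58 × 0.27 to 58 × 0.37 = 15.7 to 21.5, about 16 to 21.
- Sentence: 58 × 0.52 to 58 × 0.82 = 30.2 to 47.6, about 30 to 48.

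The gap comes from the assumed shares. It shows the mechanism and is not an estimate.

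**Upper boundary of MR (separate and minor).** The objectives in Protocol Sections 4 and 8 and SAP 4.3 give a range of 15-30%. The criteria tables in Protocol 13.3.2.2.1 and SAP 7.4.5 stop at 29%. The text of SAP 7.4.5 uses less than 30%. An unrounded decrease of 29.5% is SD under the tables and MR under the other two. A decrease of exactly 30% is PR under the criteria, yet falls inside the range in the objectives.

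**The case against.** The SAP largely deals with this already. SAP 4.3 names both proportions, the planned tables show response without and with MR, and the one place where the SAP dichotomises RECIST response puts SD on the negative side. The protocol defers detail to the SAP, and the SAP drops the sentence. SD may simply be a slip for MR. Category counts will be tabulated, so a reader could rebuild either proportion. All of this stands, and it is why the point is minor. It does not remove the contradiction. No text identifies the slip, and reading MR for SD would still describe only the second endpoint. The coding in SAP 7.4.7 is specified for a single cross-tabulation. Because MR subjects sit inside SD in the standard RECIST table, applying the protocol sentence to that table would count every CR, PR, MR and SD subject.

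A reader might infer an undocumented departure from the protocol, since Protocol 13.5 asks for changes to be recorded in the SAP and the change log entry for 7.4.5 speaks only of clarified response criteria. The documents do not support that. The log tracks changes between SAP versions, and a SAP that uses CR/PR and CR/PR/MR is following the protocol's own endpoints.

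**Conclusion.** The contradiction is real and follows from the text alone: the sentence in Protocol 13.3.2.2.1 is wrong as written against both endpoints. Its reach is limited to a descriptive secondary proportion with no alpha, threshold or sample size attached. The error would be p_SD against CR/PR and p_SD − p_MR against CR/PR/MR, both unknown here.

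Two stronger readings are not supported. One is that the trial will report stable disease as response; SAP 4.3, the two tables and SAP 7.4.7 all point the other way. The other is that the distortion is known to be large. The protocol cites a series of 15 patients with 82% stable disease and a tumor response of 0, but 0.82 × 15 = 12.3 is not a whole number, so the denominator is unclear, and that series may have used different categories. What remains is a low-severity consistency correction, worth making because it costs almost nothing.

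**What to change.** In SAP 7.4.5, state that CR or PR meets the first tumor-response endpoint; that CR, PR or MR, on the modified classification, meets the second; that SD on that classification meets neither; and that this supersedes the responder sentence in Protocol 13.3.2.2.1. Correct that sentence when the protocol is next amended.

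As a separate minor edit, define MR everywhere as a decrease of at least 15% but less than 30%: in SAP 4.3 and the SAP 7.4.5 criteria table now (the SAP 7.4.5 text already agrees), and in Protocol Sections 4, 8 and 13.3.2.2.1 at the next amendment.

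The cost is a few lines of SAP text, with no new data, tables or analyses. The protocol edits can wait, since SAP 4.1 records that enrollment is complete. These edits do not settle how unknown responses are counted or whether the proportion is by visit or by best response; those are separate questions.
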